Until now, the changes in the blood flow of the aa. uterinae during hormonal stimulation for IVF / ICSI as well as during the preparation for FET are unclear. Additionally, the "best" approach to prepare the endometrium and further on to perform a frozen embryo transfer is still not clear and the data are contradictory. This study will evaluate whether there is any change in blood flow during hormonal stimulation for IVF/ICSI and during different types of endometrial preparation for FET. In case this study would show that the blood flow of the arteria uterina right and left is influenced negatively by one of the approaches, used for endometrial preparation of the FET, then this should be taken into account in future when deciding for one or the other approach.

Methodology

A. Study Design

- Prospective cohort study, observational and unicentric (in IVIRMA Middle East Fertility Clinic, Abu Dhabi, UAE).

B. Study period and context

- Patients who are treated for primary / secondary infertility in IVIRMA Middle East Fertility Clinic, Abu Dhabi, UAE
- Estimated study duration: 6 - 8 month
- Study would start after approval of the study protocol by EC of IVIRMA Middle East Fertility Clinic Abu Dhabi.
- Study would end after inclusion of the number of patients, estimated due to the sample size calculation

C. Reference Population

Pat. with primary / secondary infertility, who undergo an ovarian stimulation treatment for IVF/ICSI and subsequently are planned for FET with vitrified embryos, either as HRT-FET or as NC-FET

D. Subject Inclusion/exclusion criteria

Inclusion criteria:

- Patients who undergo ovarian stimulation in a GnRH-antagonist protocol for IVF / ICSI
- Patients who have vitrified embryo(s)
- Preparation for FET either in HRT or NC cycle

Exclusion criteria:

- Poor responder according to Bologna criteria (Ferraretti et al.) as follows:
- At least two of the following three features must be present:
 - (i) Advanced maternal age (≥ 40 years) or any other risk factor for POR;
 - (ii) A previous POR (≤ 3 oocytes with a conventional stimulation protocol);
 - (iii) An abnormal ovarian reserve test (i.e. AFC, 5–7 follicles or AMH, 0.5 –1.1 ng/ml).
- Uterine surgery for removal of fibroids (hysteroscopic, laparoscopic) or removal of uterine septum
- Endometriosis
- Asherman-Syndrome
- Previous cytotoxic treatment
- Previous radiation of the uterus / adnexal region
- Known hypertension

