- Intake of Aspirin or similar medication which might influence the blood flow
- Status after tubal ligation
- Status after surgery in the adnexal region on 1 side

E. Intervention and Follow-up

- Patient will present themselves on day 2 / 3 of their period.

- Patients will undergo ovarian stimulation for IVF / ICSI in a GnRH-antagonist protocol: Start of stimulation medication (HMG, recFSH) on either day 2 or 3 of the cycle, dosage according to the ovarian response. From day 5 of stimulation a GnRH-antagonist will be added to prevent premature ovulation. Medication for ovulation induction (hCG, GnRH-agonist or dual trigger) will be given when at least 3 follicles are ≥ 17 mm.
- Patients will be planned for FET in either HRT or NC, according to the physician's decision.
- Factors to recommend HRT FET: irregular cycle, PCO, unavailability for treatment monitoring
- Factors to recommend NC FET: regular cycle 28 -33 days, availability for treatment monitoring

Endometrial preparation approaches:**Artificial (HRT) Cycles:**

- Commence E2 4mg from day 2/3 of period for 3 days
- Increase E2 to 6mg on day 4 of E2 treatment. E2 dose may be increased according to clinician discretion based on endometrial thickness.
- The patient will be scanned transvaginally throughout the HRT cycle to not only monitor endometrial development but to also exclude the presence of a dominant follicle on the ovaries.
- In conjunction with ultrasound monitoring the patient will undergo serial measurements of serum LH, estradiol and progesterone levels.
- Commence the initial progesterone dose of 100mg at 22hrs (vaginal suppository) after ≥ 10 days and ≤ 16 days of estradiol administration when the minimal endometrial thickness achieved is 6mm with a trilaminar appearance.
- Subsequently increase progesterone administration to 100mg vaginally three times daily. Continue estradiol administration 6mg (3 tablets daily). Embryo transfer is scheduled 5 days following the initial initiation of progesterone

Spontaneous natural cycles:

- Commencing on the second day of menses and intermittently throughout the patients' natural cycle ultrasound scans will be performed to monitor follicular growth.

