- HRT: day 2 or 3 of the cycle and day of start of progesterone administration or 1 to 2 days before in case patient will not be seen directly on the day when she starts progesterone
- NC: day 2 or 3 of the cycle and day of start of progesterone rise or 1 to 2 days before in case patient will not be seen directly on the day when progesterone starts to rise

F. Collection of biological samples and information

No biological samples will be collected for this study

Statistical methodology

A. Data base

The database will be rigorously defined with the variables destined to be analyzed according to the objectives set. The necessary information will be exported from the clinical information manager, SIVIS, to a table in Excel format through a database-based query system. The data which is not recorded in SIVIS will be collected in a password-coded EXCEL file to guarantee the data protection.

The exported data will be duly codified in order to protect the clinical and personal information of the patients according to the applicable law in the place where the research project is carried out.

Finally, and prior to the statistical study, an exploratory data analysis will be carried out to review the quality of the information extracted.

B. Study Variables

EXPOSURE VARIABLES (INDEPENDENT)

- Type of endometrial stimulation. Categorical dichotomous variable (HRT or natural cycle)

MAIN-OUTCOME MEASURE (DEPENDENT)

- Difference in the blood flow, calculated as PI and RI, between the HRT- and the NC-FET cycles, on the day of progesterone administration / progesterone rise. Quantitative continuous variable

SECONDARY OUTCOME MEASURES (DEPENDENT)

- δ_{S11} : Continuous quantitative variable measured as the differences between average PI value on the day of cycle start and the day of ovulation induction - 1 - 2 days.
- δ_{S12} : Continuous quantitative variable measured as the differences between average RI value on the day of cycle start and the day of ovulation induction - 1 - 2 days.
- Thickness of the lining. Continuous quantitative variable measured in millimeters (mm).
- Number of days of estradiol exposure before the embryo transfer. Discrete quantitative variable.

CONTROL VARIABLES

- Cycles days before start of progesterone administration.
- In HRT cycles: amount (mg) of administered Estradiol.
- Age of the patient
- BMI of the patient
- Number of previous pregnancies
- Number of previous C-sections
- Number of previous miscarriages

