- Smoker status: Smoking yes/no

C. Sample Size

So far, no study has been published evaluating the PI and RI of the arteria uterina between HRT- and NC-FETs.

The study of *Tekay et al.* compared the PI of the arteria uterina in a total of 57 patients in fresh ET's after ovarian stimulation and FET with HRT-preparation of the endometrium. However, this article does not study all the variables of our interest. Besides, it has low statistical power and our populations are different, so we consider that it is more convenient to carry out a pilot study to study descriptively the variables of interest in our population.

As this will be a pilot study, we plan to include 30 patients in each arm (HRT / NC), therefore we would estimate that we will have to include approximately 80 patients in total, as at the time of ovarian stimulation it will not be clear which type of FET patient will undergo later on. This approach was chosen in order not to interrupt patient recruitment. As this is expected to be a 2 : 1 recruitment (HRT : NC), an intra-group homogeneity analysis will be performed and if there are differences, patients from this group will be randomly selected for statistical analysis. Besides, in anticipation of potential participants wishing to withdraw from the study, an additional 5% of patients to the total sample will be added to cover possible losses, recruiting a total of 84 participants.

D. Statistical data analysis

EXPLORATORY DATA ANALYSIS

A statistical summary of the data collected in the study describing patient's population, cycle's most relevant parameters together with clinical results will be provided.

- Categorical variables will be presented in frequency tables, providing absolute frequencies and proportion of each level of each factor in the sample.
- Continuous variables will be summarized according the mean, standard deviation and 95%-confidence interval, all of them will be represented by diagrams or densities quartiles.

Exploratory data analysis will allow evaluating data quality and detecting anomalies.

HOMOGENEITY ANALYSIS

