Although the inclusion criteria and study design tend to preserve the homogeneity of study, it is important to ensure comparability between groups for each control variable. Since each patient is assigned to a group according to clinical criteria and not by random assignment between groups, it will be important to perform a homogeneity analysis to ensure that the effect studied may be due to the type of endometrial preparation and not to the effect that may be caused by a control variable behaving differently between the two study groups.

Consequently, categorical variables will be compared using the χ^2 test, and for quantitative variables, a t-Student test will be applied (if we can assume normality, if it is not possible, we will use the Kruskal-Wallis test).

OBJECTIVE ASSESSMENT

To assess the primary objective, and considering the descriptive nature of any pilot study, confidence intervals of 90%, 95% and 99% will be provided for the blood flow level in each group, and for the difference

between the comparison groups. A basic comparison test will also be provided on an indicative basis. In order to do this, and considering the size of the sample, we will first apply tests of the normality of the data. If these tests are favourable, a t-Student test will be applied. In case of not being able to assume normality, we will apply a non-parametric test.

We will proceed in the same way for the rest of the secondary objectives.

Work plan

Phase I: drafting of protocol ([name], [name], [name]) and review / approval through UAGI and EC approval

Phase II: Patient recruitment and follow-up ([name], [name])

Phase III: Data analysis ([name], designated statistician from UAGI)

Phase IV: Drafting and reviewing of manuscript, submission and publication ([name], [name], [name], [name], [name])

	2019											
	Jan	Feb	Mar	Apr	May	Jun	Jul	Aug	Sep	Oct	Nov	Dec
Phase I												
Phase II												
Phase III												
Phase IV												
Phase V												

	2020											
	Jan	Feb	Mar	Apr	May	Jun	Jul	Aug	Sep	Oct	Nov	Dec
Phase I												
Phase II												
Phase III												
Phase IV												
Phase V												

Ethical issues

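### Randomly dropping HRT patients cannot remove confounding and loses precision; no adjusted analysis is planned, and PCO and cycle regularity are not control variables

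*Combined protocol and SAP*

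**What the plan says.** All places are in the combined protocol and SAP.

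- **Assignment.** Under Methodology, E. Intervention and Follow-up, the physician decides between HRT and NC. The plan lists "Factors to recommend HRT FET: irregular cycle, PCO, unavailability for treatment monitoring" and "Factors to recommend NC FET: regular cycle 28 -33 days, availability for treatment monitoring".
- **Response to differences.** Statistical methodology, C. Sample Size, plans 30 patients per arm and about 80 in all, raised to 84 for losses. It expects twice as many HRT as NC patients and then says "an intra-group homogeneity analysis will be performed and if there are differences, patients from this group will be randomly selected for statistical analysis".
- **Control variables.** Section B. Study Variables lists preparation days before progesterone, estradiol amount (HRT only), age, BMI, previous pregnancies, C-sections and miscarriages, and smoking.
- **Purpose of the check.** The Homogeneity Analysis paragraph accepts that assignment is not random. It plans chi-square, t or Kruskal-Wallis tests of the control variables "to ensure that the effect studied may be due to the type of endometrial preparation" and not to a control variable.
- **Main comparison.** Objective Assessment gives 90%, 95% and 99% intervals per group and for the difference, plus an indicative t or non-parametric test. Secondary objectives are handled the same way. No regression, matching or stratification appears.
- **Doppler timing.** Scans are scheduled at two points of the FET cycle, for example "HRT: day 2 or 3 of the cycle and day of start of progesterone administration". The main outcome in Study Variables uses only the later one.

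**The concern.** The plan recognises confounding by clinical choice, but its one stated response cannot reduce it. The variables most directly tied to the choice of preparation are not examined at all. The exclusion criteria remove neither PCO nor irregular cycles, so these women can enter and will tend to receive HRT.

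Two of the listed control variables are consequences of the preparation. One is "Cycles days before start of progesterone administration", which is the length of the preparation phase and not a measure of cycle regularity. The other is estradiol amount, which exists only in the HRT group and so cannot be compared between groups.

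If PCO or irregular cycles are related to uterine artery flow, the planned analysis cannot separate that from an effect of HRT v NC. This matters because the Justification says that, if one approach looks unfavourable, "then this should be taken into account in future when deciding for one or the other approach".

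**Working it through.** **Plan's own figure.** 80 × 1.05 = 84, as stated. The plan gives no SD, effect size or power, so everything below is in units of the outcome SD.

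**Expected group sizes.** 80 at 2:1 gives 53.3 v 26.7, taken as 53 v 27. (84 at 2:1 gives 56 v 28.)

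**Precision.** SE of a difference in means = √(1/n₁ + 1/n₂).

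| HRT v NC | SE (SD units) | Change from 53 v 27 | 95% half-width |
|---|---|---|---|
| 53 v 27, all kept | 0.236 | – | 0.471 |
| 30 v 27, 23 of 53 HRT dropped (43%) | 0.265 | +12% | 0.532 |
| 27 v 27, 26 of 53 HRT dropped | 0.272 | +15% | 0.546 |

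If NC does reach 30 of 80, cutting 50 v 30 to 30 v 30 widens the half-width from 0.460 to 0.517 SD (+12%).

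**Bias before and after random selection.** The expected mean of any covariate in a simple random subset equals its mean in the full group. Bias in the unadjusted difference is slope × imbalance, so selection cannot change it in expectation. Simulations agree; their imbalances and slopes are assumed, because the documents give none:

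| Imbalance, slope (SD) | Product | Mean bias, 53 v 27 | Mean bias, HRT cut to 30 |
|---|---|---|---|
| 0.2, 0.2 | 0.04 | 0.039 | 0.039 |
| 0.5, 0.4 | 0.20 | 0.201 | 0.202 |
| 0.8, 0.6 | 0.48 | 0.481 | 0.481 |

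A second simulation used a binary factor present in 40% of HRT and 10% of NC patients, worth 0.5 SD, so the expected bias is 0.5 × 0.30 = 0.15. Mean bias was 0.151 with all patients, 0.152 after cutting HRT to 27, and 0.000 with adjustment on all patients. The empirical SEs were 0.242, 0.278 and 0.252.

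**Consequence for the interval.** At 53 v 27, coverage of the unadjusted 95% interval for the preparation effect (noncentral t, 78 df, noncentrality = bias/0.236) is 95%, 87% and 48% for bias 0.04, 0.20 and 0.48 SD.

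**The homogeneity test as trigger.** For a continuous covariate at 53 v 27, the t test detects imbalances of 0.2, 0.5 and 0.8 SD with power 13%, 55% and 92%. It can therefore miss imbalances that matter. This does not carry over to a strong binary imbalance: with no PCO/irregular women in NC and 40% or more in HRT, a chi-square test would detect it almost always. For PCO, the trouble is that it is not on the list.

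**Price of adjusting.** Suppose no NC patient is PCO/irregular. The adjusted contrast then rests on the regular-cycle HRT women against NC:

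| PCO/irregular in HRT | Regular HRT | SE | Change from 0.236 |
|---|---|---|---|
| 40% | 32 | √(1/32 + 1/27) = 0.261 | +11% |
| 60% | 21 | √(1/21 + 1/27) = 0.291 | +23% |
| 80% | 11 | √(1/11 + 1/27) = 0.358 | +51% |

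**Gain from the day 2/3 value.** The SE is multiplied by about √(1 − r²): 0.954, 0.866 and 0.714 for assumed correlations of 0.3, 0.5 and 0.7. At 60% PCO/irregular, 0.291 becomes 0.278, 0.252 or 0.208. At r = 0.7 this more than recovers the loss.

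**The case against.** **The selection sentence may only trim to 30 per arm.** It is introduced by the 2:1 expectation, says intra-group, does not define the group, and never claims to reduce confounding. This is a fair reading. On it, the rule itself costs only precision. But the trigger is a finding of differences, the comparison does not need equal groups, and the plan then has no response to imbalance at all.

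**Confounding is not shown.** Nothing in the documents says that PCO, cycle regularity or availability affects PI or RI. That is right, and the bias and coverage figures are illustrations. That selection leaves bias unchanged does not depend on them, and without recording these factors nobody can find out.

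**Some confounding is already controlled.** The exclusions cover hypertension, aspirin and similar drugs, endometriosis and relevant surgery. That stands and helps, but it leaves the plan's own selection factors untouched.

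**The cure may be less precise than the trimming.** At 60% or 80% PCO/irregular the adjusted SE (0.291, 0.358) exceeds that after trimming, and the restricted comparison has 21 or 11 HRT women. This is a real cost. It reflects how little the data can say about preparation when the groups barely overlap.

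**The primary aim mentions both scan days.** It does, but the main outcome definition uses only the progesterone day.

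**This is a descriptive pilot with an indicative test.** That limits the harm. The intervals for the difference still carry the same bias as the test, and the plan itself seeks attribution to the preparation.

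**Conclusion.** The concern holds and should be fixed. Random selection leaves expected imbalance and bias unchanged and, at the plan's own 2:1 split of 80, raises the standard error by 12% to 15%. No adjusted estimate is planned, and the homogeneity check omits all three named selection factors. These conclusions rest on the text and on simple arithmetic, reading the group to be sampled as HRT, the expected surplus. The size of the bias is unknown: 0.04 to 0.48 SD follows from assumed slopes of 0.2 to 0.6 and imbalances of 0.2 to 0.8 SD. The pilot status lowers the stakes but does not repair the analysis.

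**What to change.** 1. **Sample Size.** Replace the random-selection sentence with: *Recruitment is expected to be about 2:1 (HRT:NC). All evaluable patients in both groups will be analysed.* Use an interval that allows unequal group sizes and variances, such as Welch.
2. **Control variables.** Add PCO (yes/no), cycle regularity (yes/no) and the recorded reason for choosing HRT or NC, which also captures availability for monitoring.
3. **Objective Assessment.** Beside the unadjusted difference, prespecify an adjusted HRT-NC difference in mean PI and mean RI, whatever the homogeneity p-values. Use a short fixed list: PCO/irregular cycle, age, BMI, and the FET-cycle day 2/3 value of the same index if scanned before the first estradiol dose. Add a comparison restricted to regular-cycle women without PCO.
4. **Overlap.** Report the number of PCO/irregular women in each group. State that, if NC has few or none, the adjusted estimate rests on regular-cycle women and supports no causal reading for the others.
5. **Preparation-phase days and estradiol amount.** Report these descriptively, not as homogeneity or adjustment variables.

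The cost is SAP wording and three data fields, which can go in the Excel file the plan already provides for items not held in SIVIS. No extra scans or patients are needed to report these estimates. The statistical cost is a wider interval when overlap is poor (SE 0.26 to 0.36 SD against 0.236 unadjusted), before any gain from the day 2/3 value.

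### With 2:1 groups expected, the plan should name the Welch t-test and Welch intervals: a Student t-test, read as pooled, loses its nominal coverage if the arms differ in spread

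*Combined protocol and SAP*

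**What the plan says.** Under Statistical data analysis, Objective assessment, the intervals come first: "confidence intervals of 90%, 95% and 99% will be provided for the blood flow level in each group, and for the difference" between the groups. The test is secondary: "A basic comparison test will also be provided on an indicative basis". The choice of test depends on normality alone. On one branch, "If these tests are favourable, a t-Student test will be applied"; on the other, "In case of not being able to assume normality, we will apply a non-parametric test". The secondary objectives are to be handled in the same way. Unequal variances are not mentioned, and no interval formula is given.

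The Sample Size section sets the target: "As this will be a pilot study, we plan to include 30 patients in each arm (HRT / NC"). It then arrives at a larger total: "we would estimate that we will have to include approximately 80 patients in total", raised by 5% to 84 for losses. On balance it says: "As this is expected to be a 2 : 1 recruitment (HRT : NC"). The same sentence provides for a homogeneity analysis and, if that shows differences, for random selection of patients for the analysis. It does not say how many would be kept.

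The Homogeneity analysis section states that patients are assigned by clinical criteria and not at random.

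**The concern.** A pooled t-test uses one common variance estimate, dominated by the larger group. With equal groups this does little harm when the SDs differ. At 2:1 the standard error of the difference is wrong: too small if the smaller group is the more variable one, too large if the larger group is.

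The intervals for the difference are the main product of this pilot, and it is their coverage that would be off. The same holds for the secondary outcomes that compare HRT with NC, namely lining thickness and days of estradiol exposure.

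Nothing in the design secures equal spread. Assignment is not random, and the recommended cycle type depends on patient characteristics: irregular cycles and PCO point to HRT, regular cycles to NC. The Sample Size section also says that no published study has compared the two arms on PI and RI.

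**Working it through.** **Inputs from the plan.** Total 80 before losses, 5% added, expected split 2:1, target 30 per arm, confidence levels 90%, 95% and 99% (taken as two-sided).

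**The plan's own figure.** 80 × 1.05 = 84, as stated. At 2:1, 80 gives 53.3 : 26.7 (about 53:27) and 84 gives 56:28.

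**Assumed.** The documents give no SD for PI or RI in either arm, so NC:HRT SD ratios from 0.5 to 2 are used as a range. Data are taken as normal, which is the branch on which the plan uses the t-test.

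**Step 1: standard error.** With n₁ HRT and n₂ NC patients and SDs s₁ and s₂:

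- true variance of the difference = s₁²/n₁ + s₂²/n₂
- pooled variance (on average) = [((n₁−1)s₁² + (n₂−1)s₂²)/(n₁+n₂−2)] × (1/n₁ + 1/n₂)

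At 56:28 with s₁ = 1 and s₂ = 2:

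- true: 1/56 + 4/28 = 0.1607
- pooled: [(55 × 1 + 27 × 4)/82] × (1/56 + 1/28) = 1.988 × 0.05357 = 0.1065
- standard error ratio, pooled to true: √(0.1065/0.1607) = 0.81

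The same formula with s₁ = 2 and s₂ = 1 gives √(0.1614/0.1071) = 1.23. At 30:30 the pooled and true variances agree on average for any s₁ and s₂: both equal (s₁² + s₂²)/30.

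**Step 2: coverage.** Simulation with 400,000 replicates per cell, at 56:28, of the pooled interval and the Welch interval (separate variances, Satterthwaite degrees of freedom). Coverage is 100% minus the simulated error rate.

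| NC:HRT SD ratio (assumed) | Pooled 90% | Pooled 95% | Pooled 99% | Welch 95% |
|---|---|---|---|---|
| 2 | 81.9 | 88.9 | 96.4 | 95.0 |
| 1.5 | 85.1 | 91.5 | 97.7 | 95.0 |
| 1.25 | 87.3 | 93.2 | 98.4 | 95.0 |
| 1 | 90.0 | 95.0 | 99.0 | 95.0 |
| 0.8 | 92.3 | 96.5 | 99.4 | 95.0 |
| 0.67 | 93.8 | 97.4 | 99.6 | 95.0 |
| 0.5 | 95.5 | 98.3 | 99.8 | 95.0 |

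Welch is also on target at the other two levels: error 9.94–10.03% at nominal 10% and 0.98–1.02% at nominal 1%.

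**Step 3: other splits.** Range of pooled 95% coverage over NC:HRT SD ratios from 2 to 0.5:

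- 53:27: 89.1% to 98.2%
- 50:30: 90.7% to 97.6%
- 30:27: 94.0% to 95.5%
- 30:28: 94.3% to 95.4%
- 30:30: 94.8% to 95.0%

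**Step 4: cost of Welch when the SDs are equal.** At 56:28 the 95% interval is 0.6% wider on average (width ratio 1.006). Power at an assumed standardised difference of 0.66 is 80.1% against 80.6%, a loss of about 0.5 points.

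**The case against.** The strongest reply is that the plan aims for 30 per arm and foresees the imbalance: patients may be randomly selected before analysis. If that led to about 30:30, or to 30:27 or 30:28, the pooled interval would be close to nominal at every ratio tried. This stands. But the selection happens only if the homogeneity analysis shows differences, and its size is not stated. An unbalanced analysis therefore remains a planned path.

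Second, pooling is inferred from the name of the test, and the plan never ties the intervals to a pooled variance. This also stands. If the sponsor already intends unequal-variance methods, the edit only records that.

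Third, the SD ratios are assumptions. At 1.25 the shortfall is under two points, and nothing in the documents suggests a two-fold difference. This too is correct, but Welch does not need unequal spread to be shown, and equal spread is no better supported.

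A reader might go further and infer that NC must be the more variable arm, because its scans follow spontaneous hormonal events while HRT follows a set estradiol schedule, so that the intervals would be too narrow. The documents do not support this. The Intervention section lets the clinician raise the estradiol dose and lets estradiol run from 10 to 16 days before progesterone. The scan window of 1 to 2 days applies to both arms. Irregular-cycle and PCO patients are steered to HRT, which could make that arm the more variable one and the intervals too wide.

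Finally, the test is indicative, no decision rule rests on it, and the separate group summaries would reveal unequal spread. That limits the severity. It does not correct the interval for the difference.

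**Conclusion.** The point holds as a cheap improvement of low to moderate severity. Under the usual reading of Student's test, and if the analysis stays near 2:1, pooled 95% coverage departs from nominal by about 2 to 6 points downward for NC:HRT SD ratios of 1.25 to 2, and by about 1.5 to 3 points upward for ratios of 0.8 to 0.5. These sizes rest on assumed ratios and normal data. Neither the presence nor the direction of unequal spread can be established from the documents, so it would be wrong to conclude that the planned intervals are too narrow. Nor does the choice of variance formula deal with confounding from non-random assignment, which is a separate matter.

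**What to change.** In Objective assessment, replace the Student t-test with the Welch (unequal-variance) t-test. State that the 90%, 95% and 99% intervals for the difference between HRT and NC are Welch intervals. Apply this to the primary outcome and to the secondary outcomes that compare HRT with NC. No preliminary test of equal variances is needed.

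The edit is a sentence, with no extra data or patients. Its price, if the SDs are in fact equal, is the slightly wider interval and small loss of power shown in Step 4.
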